7.4. Gilead Reporting Requirements

Depending on relevant local legislation or regulations, including the applicable US FDA Code of Federal Regulations, the EU Clinical Trials Directive (2001/20/EC) and relevant updates, and other country-specific legislation or regulations, Gilead may be required to expedite to worldwide regulatory agencies reports of SAEs, serious adverse drug reactions (SADRs), or suspected unexpected serious adverse reactions (SUSARs). In accordance with the EU Clinical Trials Directive (2001/20/EC), Gilead or a specified designee will notify worldwide regulatory agencies and the relevant IEC in concerned Member States of applicable SUSARs as outlined in current regulations.

Assessment of expectedness for SAEs will be determined by Gilead using reference safety information specified in the investigator's brochure or relevant local label as applicable.

All investigators will receive a safety letter notifying them of relevant SUSAR reports associated with any study drug. The investigator should notify the IRB or IEC of SUSAR reports as soon as is practical, where this is required by local regulatory agencies, and in accordance with the local institutional policy.

7.5. Toxicity Management

7.5.1. Dose Adjustments

There is no option of SOF/VEL dose reduction due to toxicity. If SOF/VEL is withheld due to toxicity, the subject must discontinue treatment and complete an Early Termination (ET) visit.

Dose reduction or discontinuation of RBV due to toxicity is allowed at the discretion of the investigator. Once discontinued or reduced, the RBV dosing may be restarted or increased to the starting dose at the discretion of the investigator. RBV may be permanently discontinued due to toxicity without stopping SOF/VEL FDC.

7.5.2. Management of Rejection

The diagnosis of ACR, based on liver biopsy, and the decision to treat are important concerns due to the potential interactions between immunosuppression and the success of HCV treatment. It is expected that this will not be a common occurrence in this study, given that subjects must be stable and at least 6 months from transplant at study entry. Sites will be asked to follow their institutional guidelines for the management of organ rejection, but to also give consideration to the following issues as related to this study protocol. (This information is provided for guidance and consistency across subjects, but variations will not be considered protocol violations if the treatment is consistent with the guidelines of the institution).

- It is important to use standard criteria for diagnosis of rejection, to avoid over-treatment of milder grades of rejection with corticosteroids whenever possible, and to standardize the exposure to corticosteroids when treatment for rejection is necessary

- Episodes of rejection will be recorded on the CRF and severity will be graded (grading by Banff criteria, [Appendix 3](#))
- It is preferred that mild ACR is to be treated with upward adjustment of maintenance immunosuppression rather than the addition of corticosteroids
- Cases of moderate or severe ACR may require treatment with corticosteroids
- Cases of presumptive rejection should be confirmed by liver biopsy (as per standard practice) if more than one dose of corticosteroid is required
- Subjects with steroid-resistant ACR should be discontinued from the study so that management of their organ rejection can be the primary focus of treatment.

7.6. Special Situations Reports

7.6.1. Definitions of Special Situations

Special situation reports include all reports of medication error, abuse, misuse, overdose, reports of adverse events associated with product complaints, occupational exposure with an AE, pregnancy reports regardless of an associated AE and AE in an infant following exposure from breastfeeding.

Medication error is any unintentional error in the prescribing, dispensing, or administration of a medicinal product while in the control of the health care provider, subject, or consumer.

Abuse is defined as persistent or sporadic intentional excessive use of a medicinal product by a subject.

Misuse is defined as any intentional and inappropriate use of a medicinal product that is not in accordance with the protocol instructions or the local prescribing information.

An overdose is defined as an accidental or intentional administration of a quantity of a medicinal product given per administration or cumulatively which is above the maximum recommended dose as per protocol or in the product labelling (as it applies to the daily dose of the subject in question). In cases of a discrepancy in drug accountability, overdose will be established only when it is clear that the subject has taken the excess dose(s). Overdose cannot be established when the subject cannot account for the discrepancy except in cases in which the investigator has reason to suspect that the subject has taken the additional dose(s).

Product complaint is defined as complaints arising from potential deviations in the manufacture, packaging, or distribution of the medicinal product.

Occupational exposure with an AE is defined as exposure to a medicinal product as a result of one's professional or non-professional occupation

7.6.2. Instructions for Reporting Special Situations

7.6.2.1. Instructions for Reporting Pregnancies

The investigator should report pregnancies in female study subjects that are identified after initiation of study drug and throughout the study, including the post study drug follow-up period, to Gilead DSPH using the pregnancy report form within 24 hours of becoming aware of the pregnancy.

Refer to Section 7.3 and the CRF/eCRF completion guidelines for full instructions on the mechanism of pregnancy reporting.

The pregnancy itself is not considered an AE nor is an induced elective abortion to terminate a pregnancy without medical reasons.

Any premature termination of pregnancy (eg, a spontaneous abortion, an induced therapeutic abortion due to complications or other medical reasons) must be reported within 24 hours as an SAE. The underlying medical reason for this procedure should be recorded as the AE term.

A spontaneous abortion is always considered to be an SAE and will be reported as described in Section 7.1.2. Furthermore, any SAE occurring as an adverse pregnancy outcome post study must be reported to Gilead DSPH.

The subject should receive appropriate monitoring and care until the conclusion of the pregnancy. The outcome should be reported to Gilead DSPH using the pregnancy outcome report form. If the end of the pregnancy occurs after the study has been completed, the outcome should be reported directly to Gilead DSPH. Gilead DSPH contact information is as follows: Email: PPD and Fax: PPD

Pregnancies of female partners of male study subjects exposed to Gilead or other study drugs must also be reported and relevant information should be submitted to Gilead DSPH using the pregnancy and pregnancy outcome forms within 24 hours. Monitoring of the subject should continue until the conclusion of the pregnancy. If the end of the pregnancy occurs after the study has been completed, the outcome should be reported directly to Gilead DSPH, fax number PPD or email PPD

Refer to Appendix 4 for Pregnancy Precautions, Definition for Female of Childbearing Potential, and Contraceptive Requirements.

7.6.2.2. Reporting Requirements for Liver Transplant and Complications of Liver Transplant

If the liver transplant procedure occurs within the AE collection window (30 days after the last dose of study drug), due to the nature of the subject population and the inclusion criteria, events that are clearly related to liver transplant should not be collected as an AE or SAE. In addition, these events will be exempt from global expedited reporting requirements for the duration of the study. These include:

- a) The liver transplant procedure itself (and related hospitalization)

- b) Events that are direct sequelae of the liver transplant (such as surgical complications) or peri-operative care (central line insertions, etc.)
- c) Planned hospitalizations for testing or procedures that are part of the liver transplant assessment and preparation process

These events should be reported as AEs/SAEs only if it is assessed that the events were not an anticipated or predictable part of the transplant process or procedure. In addition, concomitant medications related to the transplant procedure do not need to be recorded (anesthetics, peri-operative pain medication, etc). If there are any questions about how an event should be reported, please contact the study Medical Monitor.

7.6.2.3. Reporting Other Special Situations

All other special situation reports must be reported on the special situations report form and forwarded to or Gilead DSPH within 24 hours of the investigator becoming aware of the situation. These reports must consist of situations that involve study drug and/or Gilead concomitant medications, but do not apply to non-Gilead concomitant medications.

Special situations involving non-Gilead concomitant medications does not need to be reported on the special situations report form; however, for special situations that result in AEs due to a non-Gilead concomitant medication, the AE should be reported on the AE form.

Any inappropriate use of concomitant medications prohibited by this protocol should not be reported as “misuse,” but may be more appropriately documented as a protocol deviation.

Refer to Section 7.3 and the CRF/eCRF completion guidelines for full instructions on the mechanism of special situations reporting.

All clinical sequelae in relation to these special situation reports will be reported as AEs or SAEs at the same time using the AE CRF/eCRF and/or the SAE report form. Details of the symptoms and signs, clinical management, and outcome will be reported, when available.

8. STATISTICAL CONSIDERATIONS

8.1. Analysis Objectives and Endpoints

8.1.1. Analysis Objectives

The primary objectives of this study are:

- To evaluate the efficacy of treatment with sofosbuvir (SOF)/velpatasvir (VEL) fixed-dose combination (FDC) with ribavirin (RBV) for 12 weeks in subjects with chronic HCV infection and Child-Pugh-Turcotte (CPT) class C cirrhosis as measured by the proportion of subjects with sustained viral response 12 weeks after cessation of treatment (SVR12)
- To evaluate the safety and tolerability of the treatment regimen

The secondary objectives of this study are:

- To determine the proportion of subjects who attain SVR at 4 and 24 weeks after cessation of the study treatment regimen (SVR4 and SVR24)
- To evaluate the proportion of subjects with virologic failure
- To evaluate therapeutic efficacy as measured by the change of CPT score and MELD score
- To evaluate the kinetics of circulating HCV RNA during treatment and after cessation treatment
- To evaluate the emergence of viral resistance to SOF and VEL during treatment and after cessation of treatment

The exploratory objectives of this study are:

PPD

8.1.2. Primary Endpoint

The primary efficacy endpoint is SVR12 (HCV RNA < LLOQ 12 weeks after cessation of study treatment regimen) in the Full Analysis Set (FAS).

The primary safety endpoint is any AE that led to permanent discontinuation of study drug.

8.1.3. Secondary Endpoint

The secondary efficacy endpoints include the proportion of subjects who attain sustained virologic response at 4 and 24 weeks after cessation of the study treatment regimen (SVR4 and SVR24); the proportion of subjects who have HCV RNA < LLOQ by visit while on study treatment; CPT and MELD score changes from Day 1; absolute and change from Day 1 in HCV RNA through Week 12; and the proportion of subjects with virologic failure.

8.1.4. Other Endpoints of Interest

Other endpoints of interest may include ALT normalization and change in HRQoL parameters.

8.2. Analysis Conventions

All individual subject data will be listed as measured. All statistical summaries and analyses will be performed using SAS[®] software (SAS Institute, Cary, North Carolina, USA).

The study drugs in this study are SOF/VEL + RBV. Last dose of the study drug refers to the last dose of SOF/VEL and RBV and will be used in the definition of treatment-emergent AEs and laboratory abnormalities as well as the efficacy endpoints of SVR at various posttreatment timepoints.

8.2.1. Analysis Sets

8.2.1.1. Efficacy Analysis Set

The analysis set for antiviral activity analyses is defined as the Full Analysis Set (FAS) which includes all enrolled subjects who received at least 1 dose of the study drug.

8.2.1.2. Safety Analysis Set

The primary analysis set for safety analyses will be Safety Analysis Set which includes all subjects who took at least 1 dose of the study drug.

Treatment-emergent data will be analyzed and defined as data collected from the first dose of the study drug through the date of the last dose of the study drug plus 30 days.

8.2.1.3. Pharmacokinetics Analysis Sets

The Pharmacokinetic (PK) Analysis Set includes all enrolled subjects who took at least 1 dose of study drug and have at least 1 nonmissing postdose concentration value for the corresponding analyte in plasma. The analytes of interest may include SOF (and its metabolites GS-566500 and GS-331007), VEL, and RBV. The PK Analysis Set will be used for analysis of general PK.

8.2.2. Data Handling Conventions

Missing data can have an impact upon the interpretation of the trial data. Other than the endpoints discussed below, values for missing data will not be imputed.

For the analyses of categorical HCV RNA data, missing posttreatment HCV RNA data will have the missing data imputed. Missing on-treatment HCV RNA will have the missing data imputed up to the time of the last dose.

If a data point is missing and is preceded and followed in time by values that are “< LLOQ target not detected (TND),” then the missing data point will be set to “< LLOQ TND.” If a data point is missing and preceded and followed by values that are “< LLOQ detected,” or preceded by “< LLOQ detected” and followed by “< LLOQ TND,” or preceded by “< LLOQ TND” and followed by “< LLOQ detected,” then the missing value will be set to “< LLOQ detected.” In these situations the data point will be termed a bracketed success; otherwise, the data point will be termed a bracketed failure (ie, \geq LLOQ detected). If a data point is missing and is not bracketed, the missing data point will also be termed a failure (ie, \geq LLOQ detected).

Where appropriate, safety data for subjects that did not complete the study will be included in summary statistics. For example,

- If a subject took at least 1 dose of study drug, the subject will be included in a summary of AEs according to the treatment received; otherwise, if the subject is not dosed, then they will be excluded from the summary.
- If safety laboratory results for a subject are missing for any reason at a time point, the subject will be excluded from the calculation of summary statistics for that time point. If the subject is missing a pre-dose value, then the subject will be excluded from the calculation of summary statistics for the predose value and the change from predose values.

Values for missing safety laboratory data will not be imputed; however, a missing Day 1 result will be replaced with a screening result, if available. If no pretreatment laboratory value is available, the Day 1 value will be assumed to be normal (ie, no grade [Grade 0]) for the summary of graded laboratory abnormalities.

Values for missing vital signs data will not be imputed; however, a missing Day 1 result will be replaced with a screening result, if available.

HCV RNA values below the LLOQ for the assay will be set to the lower limit minus 1 for calculation of summary statistics for the actual HCV RNA values and the change from Day 1 values by study visit. The reported values will be provided in the HCV RNA listing.

For selected analyses of early time point data, HCV RNA data (IU/mL) may be transformed to the logarithmic (base 10) scale (\log_{10} IU/mL).

8.3. Demographic Data and Baseline Characteristics

Demographic and baseline measurements will be summarized using standard descriptive methods.

Demographic data will include sex, self-identified race/ethnicity.

Baseline characteristic data will include body mass index, HCV RNA level (\log_{10} IU/mL), genotype of HCV infection, IL28B genotype, CPT score, MELD score and additional endpoints as necessary.

8.4. Efficacy Analysis

[figure not shown]
8.4.1. Primary Analysis

The primary efficacy endpoint for this study will be the proportion of subjects with SVR12, defined as HCV RNA < LLOQ 12 weeks after cessation of the study treatment regimen in the FAS population. Point estimate and 95% confidence interval (using the Clopper-Pearson method) of SVR12 will be computed.

8.4.2. Secondary Analyses

The proportion of subjects with HCV RNA below the LLOQ over time (including SVR4 and SVR24) will be presented in tabular and graphical form. Descriptive summaries and listings will be provided for additional efficacy evaluations of the proportion of subjects who experience virologic failure, serum HCV RNA actual values and change from baseline, and other endpoint of interest including ALT normalization.

PPD

Details on efficacy analyses will be described in the statistical analysis plan.

8.5. Safety Analysis

Safety will be evaluated by assessment of clinical laboratory tests, physical examinations, vital signs measurements and AEs which will be documented at various time points during the study.

All safety data collected on or after the first dose of the study drug administration up to 30 days after the last dose of the study drug will be summarized.

8.5.1. Extent of Exposure

A subject's extent of exposure to the study drug will be generated from the study drug administration page of eCRF. Exposure data will be summarized.

8.5.2. Adverse Events

Clinical and laboratory adverse events will be coded using the Medical Dictionary for Regulatory Activities (MedDRA). System Organ Class (SOC), High-Level Group Term (HLGT), High-Level Term (HLT), Preferred Term (PT), and Lower-Level Term (LLT) will be attached to the clinical database.

Events will be summarized on the basis of the date of onset for the event. A treatment-emergent adverse event will be defined as any adverse event with an onset date on or after the study drug start date and no later than 30 days after permanent discontinuation of the study drug or any adverse event leading to premature discontinuation of the study drug.

Summaries (number and percentage of subjects) of treatment-emergent adverse events (by SOC and PT) will be provided for:

- All AEs
- AEs of Grade 3 or above
- AEs of Grade 2 or above
- All treatment-related AEs
- Treatment-related AEs of Grade 3 or above
- Treatment-related AEs of Grade 2 or above
- All SAEs
- All treatment-related SAEs
- All AEs leading to premature discontinuation of the study drug
- Deaths

All AEs collected during the study will be presented in the data listings

8.5.3. Laboratory Evaluations

Selected laboratory data (using conventional units) will be summarized (n, mean, SD, median, Q1, Q3, minimum, and maximum) by study visit along with the corresponding change from Baseline/Day 1.

Graded laboratory abnormalities will be defined using the laboratory toxicity grading scheme defined in [Appendix 3](#).

Incidence of treatment-emergent laboratory abnormalities, defined as values that increase by at least one toxicity grade from baseline at any time post baseline up to and including the date of last dose of study drug plus 30 days will be summarized.

Values for missing safety laboratory data will not be imputed; however, a missing Baseline/Day 1 result will be replaced with a screening result, if available. If no pretreatment laboratory value is available, the baseline value will be assumed to be normal (ie, no grade [Grade 0]) for the summary of graded laboratory abnormalities. If Baseline/Day 1 data are missing, then any post-baseline graded abnormality (ie, at least Grade 1) will be considered treatment emergent.

All laboratory abnormalities will be included in the listings of laboratory data.

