3.4.2. Toxicity-Based Stopping Criteria

Subjects who meet any of the following laboratory or adverse event criteria must stop treatment with SOF/VEL:

- Confirmed total bilirubin > 3x Day 1 or nadir and ALT and/or AST > 3x Day 1 or nadir
- Elevation of alanine aminotransferase (ALT) and/or aspartate aminotransferase (AST) > 10x Day 1 or nadir, confirmed by immediate repeat testing
- Elevation of ALT >15x ULN, confirmed by immediate repeat testing
- Any Grade 3 or greater rash associated with constitutional symptoms
- Any non-laboratory Grade 4 event assessed as related to administration of SOF/VEL, study drugs should be discontinued immediately

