4.2. Inclusion Criteria

Subjects must meet all of the following inclusion criteria to be eligible for participation in this study.

- 1) Willing and able to provide written informed consent
- 2) Males and females, age ≥ 18 years old
- 3) A body mass index (BMI) of ≥ 18 kg/m²
- 4) Chronic HCV infection (≥ 6 months) as documented by either prior medical history or liver biopsy
- 5) Quantifiable HCV RNA at Screening
- 6) Subjects may be non-transplanted or with recurrent HCV post-liver transplant.
 - a. If listed for liver transplant, then the projected date of transplant must be ≥ 12 weeks after Day1 of treatment
 - b. If post-liver transplant, then Day1 must be ≥ 6 months from date of transplant
- 7) CPT score of 10 to 12, inclusive, as determined at Screening
- 8) Liver imaging within 6 months of Day 1 to exclude HCC
- 9) If treatment-experienced, the most recent HCV treatment must have been completed at least 8 weeks prior to Screening
- 10) Females of childbearing potential (as defined in [Appendix 4](#)) must have a negative serum pregnancy test at Screening and a negative urine pregnancy test on Day 1 prior to randomization

- 11) Male subjects and female subjects of childbearing potential who engage in heterosexual intercourse must agree to use protocol specified method(s) of contraception as described in [Appendix 4](#)
- 12) Female subjects must agree to refrain from egg donation and in vitro fertilization during treatment until at least 30 days after the last dose of SOF/VEL or 6 months after the last dose of RBV, whichever occurs last
- 13) Lactating females must agree to discontinue nursing before the study drugs are administered
- 14) Male subjects must agree to refrain from sperm donation from the date of Screening until at least 7 months after the last dose of RBV or 30 days after the last dose of SOF/VEL, whichever occurs last
- 15) Subject must be able to comply with the dosing instructions for study drug administration and able to complete the study schedule of assessments

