 - e) Alkaline phosphatase > 10 \times ULN
 - f) Sodium < 125 mEq/L
 - g) Total bilirubin > 10 mg/dL
 - h) Creatinine clearance (CL_{cr}) < 30 mL /min, as calculated by the Cockcroft-Gault equation {[Cockcroft et al 1976](#)} using actual body weight
- 14) Hepatitis B surface antigen positive (HBsAg+) at Screening
- 15) Infection with human immunodeficiency virus (HIV)

- 16) Clinically-relevant alcohol or drug abuse within 12 months of screening. A positive drug screen will exclude subjects unless it can be explained by a prescribed medication; the diagnosis and prescription must be approved by the Investigator.
- 17) Prior exposure to any HCV NS5A inhibitor
- 18) Current use of corticosteroids at any dose >10 mg of prednisone/day (or equivalent dose of corticosteroid)
- 19) Use of any prohibited concomitant medications as described in Section 5.5
- 20) Use of GM-CSF, epoetin alfa or other hematopoietic stimulating agents within 2 weeks of Screening.
- 21) Male with pregnant female partner.
- 22) History of clinically significant hemoglobinopathy (eg, sickle cell disease, thalassemia)
- 23) Contraindications to RBV therapy
- 24) Known hypersensitivity to VEL, RBV, SOF, the metabolites, or formulation excipients
- 25) Participation in a clinical study with an investigational drug or biologic within 3 months prior to Day 1

Exclusion criteria that are specific to subjects who have not had a liver transplant

- 26) Medical justification for any MELD exception points (such as for HCC, current hepatopulmonary syndrome, intractable encephalopathy, or any other reason)
- 27) History of hepatopulmonary syndrome

Exclusion criteria that are specific to subjects who have had a liver transplant

- 28) Recipient of ABO incompatible organ
- 29) Histological evidence of unresolved rejection of liver transplant
- 30) Patients who had evidence of HCC at time of transplant must be 5 years posttransplant with no evidence of recurrence at Screening
- 31) Use or planned use of T-cell depleting/masking antibodies, systemic antineoplastic agents or cyclosporine >300mg/day, or use of any prohibited medications listed in Section 5.4

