Hypocalcemia (corrected for albumin if appropriate*) Adult and Pediatric ≥2 Years	7.8 <LLN mg/dL 1.94 to <LLN mmol/L	7.0 to < 7.8 mg/dL 1.74 to < 1.94 mmol/L	6.1 to < 7.0 mg/dL 1.51 to < 1.74 mmol/L	< 6.1 mg/dL < 1.51 mmol/L
Pediatric ≥7 days -2 Years	7.8 to 8.4 mg/dL 1.94 to 2.10 mmol/L	7.0 to <7.8 mg/dL 1.74 to <1.94 mmol/L	6.1 to <7.0 mg/dL 1.51 to < 1.74 mmol/L	< 6.1 mg/dL < 1.51 mmol/L
Infant, < 7 Days	6.5 to 7.5 mg/dL 1.61 to 1.88 mmol/L	6.0 to < 6.5 mg/dL 1.49 to < 1.61 mmol/L	5.5 to < 6.0 mg/dL 1.36 to < 1.49 mmol/L	< 5.5 mg/dL < 1.36 mmol/L
Hypercalcemia (corrected for albumin if appropriate*) Adult and Pediatric ≥ 7 Days	>ULN to 11.5 mg/dL >ULN to 2.88 mmol/L	> 11.5 to 12.5 mg/dL > 2.88 to 3.13 mmol/L	> 12.5 to 13.5 mg/dL > 3.13 to 3.38 mmol/L	> 13.5 mg/dL > 3.38 mmol/L
Infant, < 7 Days	11.5 to 12.4 mg/dL 2.86 to 3.10 mmol/L	> 12.4 to 12.9 mg/dL > 3.10 to 3.23 mmol/L	> 12.9 to 13.5 mg/dL > 3.23 to 3.38 mmol/L	> 13.5 mg/dL > 3.38 mmol/L
Hypocalcemia (ionized)	3.0 mg/dL to < LLN 0.74 mmol/L to < LLN	2.5 to < 3.0 mg/dL 0.62 to < 0.74 mmol/L	2.0 to < 2.5 mg/dL 0.49 to < 0.62 mmol/L	< 2.0 mg/dL < 0.49 mmol/L
Hypercalcemia (ionized)	> ULN to 6.0 mg/dL > ULN to 1.50 mmol/L	> 6.0 to 6.5 mg/dL > 1.50 to 1.63 mmol/L	> 6.5 to 7.0 mg/dL > 1.63 to 1.75 mmol/L	> 7.0 mg/dL > 1.75 mmol/L
Hypomagnesemia	1.40 to <LLN mg/dL 1.2 to <LLN mEq/L 0.58 to <LLN mmol/L	1.04 to < 1.40 mg/dL 0.9 to < 1.2 mEq/L 0.43 to < 0.58 mmol/L	0.67 to < 1.04 mg/dL 0.6 to < 0.9 mEq/L 0.28 to < 0.43 mmol/L	< 0.67 mg/dL < 0.6 mEq/L < 0.28 mmol/L

CHEMISTRY				
	Grade 1	Grade 2	Grade 3	Grade 4
Hypophosphatemia Adult and Pediatric > 14 Years Pediatric 1 Year–14 Years Pediatric < 1 Year	2.0 to < LLN mg/dL 0.63 to < LLN mmol/L	1.5 to < 2.0 mg/dL 0.47 to < 0.63 mmol/L	1.0 to < 1.5 mg/dL 0.31 to < 0.47 mmol/L	< 1.0 mg/dL < 0.31 mmol/L
	3.0 to < LLN mg/dL 0.96 to < LLN mmol/L	2.5 to < 3.0 mg/dL 0.80 to < 0.96 mmol/L	1.5 to < 2.5 mg/dL 0.47 to < 0.80 mmol/L	< 1.5 mg/dL < 0.47 mmol/L
	3.5 to < LLN mg/dL 1.12 to < LLN mmol/L	2.5 to < 3.5 mg/dL 0.80 to < 1.12 mmol/L	1.5 to < 2.5 mg/dL 0.47 to < 0.80 mmol/L	< 1.5 mg/dL < 0.47 mmol/L
Hyperbilirubinemia Adult and Pediatric > 14 Days Infant, ≤ 14 Days (non-hemolytic) Infant, ≤ 14 Days (hemolytic)	> 1.0 to 1.5 × ULN	> 1.5 to 2.5 × ULN	> 2.5 to 5.0 × ULN	> 5.0 × ULN
	NA	20.0 to 25.0 mg/dL 342 to 428 μmol/L	> 25.0 to 30.0 mg/dL > 428 to 513 μmol/L	> 30.0 mg/dL > 513 μmol/L
	NA	NA	20.0 to 25.0 mg/dL 342 to 428 μmol/L	> 25.0 mg/dL > 428 μmol/L

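### In the graded laboratory table, subjects whose Day 1 bilirubin is already Grade 4 cannot be counted as treatment-emergent but stay in the denominator

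*Protocol*

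**What the plan says.** Section 8.5.3 of the protocol fixes the grading source: "Graded laboratory abnormalities will be defined using the laboratory toxicity grading scheme defined in" Appendix 3. It then promises an incidence summary of treatment-emergent abnormalities, "defined as values that increase by at least one toxicity grade from baseline at any time post baseline", up to 30 days after the last dose.

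In Appendix 3 (Chemistry), the row "Hyperbilirubinemia Adult and Pediatric > 14 Days" sets Grade 3 at "> 2.5 to 5.0 × ULN". Grade 4 is everything above 5.0 times ULN, with no upper bound.

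The bilirubin entry limit, exclusion 13(g) in Section 4.3, applies at Screening and is in absolute units: "Total bilirubin > 10 mg/dL". The inclusion criteria also require a "CPT score of 10 to 12, inclusive, as determined at Screening".

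Section 8.5.3 makes one exception to the one-grade rule: "If Baseline/Day 1 data are missing, then any post-baseline graded abnormality (ie, at least Grade 1) will be considered treatment emergent". It has no rule for a subject whose recorded baseline is already the top grade. It also provides by-visit summaries of selected tests with change from baseline, and listings of all laboratory abnormalities.

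**The concern.** A one-grade rule works only if a subject can still move up a grade. The Screening limits for ALT, AST and alkaline phosphatase are 10 times ULN, exactly where Appendix 3 passes from Grade 3 to Grade 4, so a subject eligible on those tests can still rise a grade. The bilirubin limit is in mg/dL and, at usual values of the ULN, lies well inside Grade 4.

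A subject who starts there adds to the denominator of the bilirubin line and can never add to the numerator, however far bilirubin rises. The same holds for one who starts at Grade 4, improves and then rebounds to Grade 4.

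Safety and tolerability is a primary objective, and Section 1.4 justifies the study by the fact that only 4 subjects with Child-Pugh-Turcotte (CPT) class C cirrhosis had received the regimen in the earlier trial. An incidence of bilirubin worsening that can err only downward where baseline is recorded is a poor summary for that purpose.

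**Working it through.** The protocol states no figure on this point. Its 29% maximum confidence interval length for SVR12 (Section 8.7) plays no part here.

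**Inputs.** Grade 4 lower bound: 5.0 × ULN (Appendix 3). Entry ceiling: 10 mg/dL (exclusion 13(g)). The ULN is not in the document; I assume 1.0 to 1.3 mg/dL and extend the range to 2.0.

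**Step 1: does an eligible Grade 4 band exist?** It does when 5.0 × ULN < 10 mg/dL, that is, when ULN < 2.0 mg/dL. Its width is 10 − 5.0 × ULN.

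| ULN (mg/dL) | Grade 4 above (mg/dL) | Entry ceiling as multiple of ULN | Width of band (mg/dL) |
|---|---|---|---|
| 1.0 | 5.0 | 10.0 | 5.0 |
| 1.1 | 5.5 | 9.1 | 4.5 |
| 1.2 | 6.0 | 8.3 | 4.0 |
| 1.3 | 6.5 | 7.7 | 3.5 |
| 2.0 | 10.0 | 5.0 | 0 |

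**Step 2: does the CPT window close the band?** In Table 6-1, bilirubin above 3 mg/dL scores 3 points. A total of 10 to 12 then needs 7 to 9 points from the other four components, each scored 1 to 3. Of the 3⁴ = 81 combinations, 16 total 7, 19 total 8 and 16 total 9, which makes 51. The window does not close the band.

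**Step 3: what does the rule do to two comparable rises?** For any ULN from 1.0 to 1.3 mg/dL:

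- 4 to 12 mg/dL (12/4 = 3.0-fold): baseline is 3.1 to 4.0 × ULN, Grade 3; the later value is 9.2 to 12 × ULN, Grade 4. Counted.
- 7 to 21.5 mg/dL (21.5/7 = 3.07-fold): baseline is 5.4 to 7.0 × ULN, Grade 4; the later value is also Grade 4. Not counted, although it exceeds the bilirubin multiple in Section 3.4.2.

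**Step 4: how large could the effect be?** The share of subjects at Grade 4 on Day 1 is not given. As illustration only: if k of 50 start there, the highest incidence the line can show is (50 − k)/50. That is 96% for k = 2, 90% for k = 5 and 80% for k = 10. The largest possible undercount is k/50, or 4, 10 and 20 percentage points. The actual undercount depends on how many of those k subjects worsen, which is unknown.

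**The case against.** The strongest reply is that the one-grade rule is reasonable, that shift tables and fold-change counts usually belong in a statistical analysis plan, and that worsening can be seen elsewhere. Much of this stands:

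- The by-visit summaries include quartiles and change from baseline, and with about 50 subjects the listings are readable. These summaries cover only selected tests, however, and neither display gives the number of subjects who worsened.
- MELD change from Day 1 is a secondary endpoint, and bilirubin enters the score without an upper cap.
- Laboratory abnormalities that need intervention or lead to a change in study drug must be recorded as adverse events (Section 7.1.3). The primary safety endpoint, adverse events leading to permanent discontinuation, does not use the graded table.
- The stopping rule, "Confirmed total bilirubin > 3x Day 1 or nadir and ALT and/or AST > 3x Day 1 or nadir", works on fold-change and has no ceiling.

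A reader might infer that the plan is blind to hepatic worsening, or blind in its sickest subjects. The documents support neither reading. The ceiling shown here concerns bilirubin in one descriptive table. CPT severity is a five-component sum in which 3.1 and 9 mg/dL score the same, so the affected subjects are those with the highest baseline bilirubin, not demonstrably those at greatest hepatic risk.

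Nor is everyone who screens in above 5.0 × ULN affected. The limit applies at Screening, baseline is Day 1, and up to 28 days (42 with approval) may lie between, so a subject may have moved to a lower grade.

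Two further readings fail. A stopping rule for individuals and an incidence table for the group need not share a metric. A large rise within Grade 3 that goes uncounted (3.1 to 5.9 mg/dL at ULN 1.2, for example) is a feature of any graded scale.

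The appeal to an analysis plan does not remove the point. The absence of extra tables is no defect, but the counting rule itself is fixed in the protocol. Section 8.4.2 defers details of efficacy analyses to the analysis plan; Section 8.5 makes no such statement for safety.

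**Conclusion.** The point holds for one table. With a recorded Day 1 bilirubin above 5.0 × ULN, a subject cannot register a treatment-emergent bilirubin abnormality in the Section 8.5.3 incidence summary but remains in its denominator. As a measure of how many subjects worsened, that incidence is biased downward.

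This needs only a ULN below 2.0 mg/dL and at least one such subject. The specific threshold of 5.0 to 6.5 mg/dL rests on the assumed ULN of 1.0 to 1.3 mg/dL. The size of the bias cannot be computed from the documents and may be small. The missing-baseline exception is minor and works in the other direction.

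The primary safety endpoint and the stopping rule are unaffected. This is an inexpensive improvement worth making, not a flaw that threatens the trial's safety conclusions.

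**What to change.** Keep the graded incidence table. In Section 8.5.3 add, for bilirubin:

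1. The number and percentage of subjects whose post-baseline value exceeds 3 times Day 1 or nadir, alone and together with ALT and/or AST above 3 times Day 1 or nadir. This reuses the multiple in Section 3.4.2 as a descriptive threshold only.
2. A shift table of baseline grade by worst post-baseline grade.
3. A statement of how many subjects were already Grade 4 at baseline, so that readers can see how many in the denominator could not be counted.

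Appendix 2 schedules chemistry at every visit, so no new data are needed. The cost is a little programming and possibly a less favourable-looking safety display. Eligibility, dosing and stopping rules do not change.
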